This protocol template is intended for use in clinical studies which **are not** Clinical Trials of Investigational Medicinal Products (CTIMPs) that are Sponsored or Co-Sponsored by the University of Dundee and/or NHS Tayside.

All sections may be adapted to suit a particular trial/study.

Some sections may be added as required by the specific trial/study.

All blue/red instruction text is for guidance only and must be removed.

Trial/Study Protocol

Full study title: "Studying Pregnancy's VAscular and Retinal Changes" SPARC

Short Title /Study Acronym	"Studying Pregnancy's VAscular and Retinal Changes" SPARC
Sponsor	University of Dundee
Sponsor ID	2-021-25
Funder	University of Dundee
Chief Investigator	CI: [name]
Principal Investigator	PI: [name] (PhD student)
	2 nd Academic supervisor: [name]
	3d Academic supervisor: [name]
IRAS Number	347685
Version Number and Date	1.0
	13/3/2025

PROTOCOL APPROVAL

Insert trial/study title: "Studying Pregnancy's VAscular and Retinal Changes" SPARC

Signatures

The undersigned confirm that the following protocol has been agreed and approved by the Sponsor and that the Chief Investigator agrees to conduct the trial/study/study in compliance with this approved protocol and will adhere to the principles of GCP, the Sponsor SOPs, and any other applicable regulatory requirements as may be amended from time to time.

[name]	[name]	01/02/2025
Chief Investigator	Signature	Date
[name]	[name]	01/02/2025
Individual Responsible for Statistical Review	Signature	Date

LIST OF ABBREVIATIONS

AE	Adverse Event	
CI		
	Chief Investigator	
CNORIS	Clinical Negligence and Other Risks Indemnity Scheme	
CRF	Case Report Form	
DMC	Data Monitoring Committee	
GCP	Good Clinical Practice	
ICF	Informed Consent Form	
IF	Incidental Findings	
ISF	Investigator Site File	
PI	Principal Investigator	
REC	Research Ethics Committee	
SAE	Serious Adverse Event	
SOP	Standard Operating Procedures	
S/TMF/SMF	Trial Master File/Study Master File	
T/SMG	Trial Management Group	
TSC	Trial Steering Committee	

SUMMARY/SYNOPSIS

Trial/Study Title (including acronym)	Studying Pregnancy's VAscular and Retinal Changes (SPARC)	
Trial/Study Design	Prospective imaging study	
Trial/Study Population	Pregnant women	
Sample Size	P. 44	
Planned Trial/study Period	24 months	
Clinical phase duration	During Pregnancy	
Follow up phase duration or specify none	n/a	

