Primary	Objectives To investigate the potential of retinal imaging technology to assess endothelial function in women during pregnancy, in order to evaluate the effect of GH on maternal CV function.	Outcome Measures Primary Outcome Measures: 1. Retinal Vascular System 2. Endothelial Function 3. Cardiovascular Function biomarkers Secondary Outcome Measures: 1. Pregnancy-Related Health Outcomes 2. Maternal Health
Secondary	Objectives Study – Aim: Investigate whether retinal imaging is able to capture endothelial dysfunction in women who have complicated pregnancy. Endothelial function measured using retinal imaging and ultrasound pulse-wave Doppler and measured in correlation with serum biomarkers.	Outcome Measures 1. Primary Outcome Measures - Retinal Vascular Health measurements - Ultrasound Pulse-Wave Doppler Findings - Blood Biomarkers 2. Secondary Outcome Measures - Long-term Cardiovascular Risk Indicators
Optional Inclusion Criteria	Prospective imaging study 1- Women aged 18 or above 2- Women who are pregnant after 8 weeks 3- Women must be able to give written informed consent (ICF) Note: Women that are diagnosed with gestational hypertension (after 12 weeks) will be included. Includes the following hospital: NINEWELLS HOSPITAL	
Optional Exclusion Criteria	1- Maternal age less than 18 years 2- Women who are not capable of giving informed consent (ICF).	

Studying Pregnancy's VAscular and Retinal Changes (SPARC), Non CTIMP Protocol (SPARC) During Preg <v1.0 13/3/2025>; IRAS: 347685

5.Known retinal or eye disorders	 3- Pre-existing chronic hypertension or cardiovascular diseases diagnosed prior to the index pregnancy. 4. Women that have chronic hypertension at their booking visit (before 12 weeks)
hypertensive therapy, anticoagulants).	5.Known retinal or eye disorders6. Use of medications affecting endothelial function (e.g., ongoing anti-

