The test takes about 10 minutes.

Retinal imaging and ultrasound (including carotid and ophthalmic artery Doppler) will be conducted in the Tayside Clinical Research Centre/Clinical room at the Division of Cardiovascular Research (Blood Flow Lab), Corridor L, Level 7, Ninewells Hospital, by PI [name].

Blood Samples

A 20ml blood sample will be taken from the participant during the investigation/assessment. Which are (sFlts-1, PLGF and endothelin-1). The blood sample will be collected concurrently with their usual blood tests that are clinically necessary as part of their regular clinical care.

Studying Pregnancy's VAscular and Retinal Changes (SPARC), Non CTIMP Protocol (SPARC) During Preg <v1.0 13/3/2025>; IRAS: 347685

A 20ml blood sample will be taken from the participant during the investigation/assessment by trained CRC staff for study of circulating biomarkers. This is intended to be a Prospective study and will provide data for future power analysis to estimate how many women need to be recruited.

Blood samples will be collected by nurses in the Clinical Research Centre (CRC). All procedures will be completed on the same day as the examination.

Once all the measurements have been taken, there will be no further requirements or assessments. The research specific procedure results will be recorded in the CRF only.

Blood samples from both control and case will be used to assess circulating biomarkers for example but not limited to sFlt-1 & PLGF (clinically used to diagnose preeclampsia), endothelin-1 (marker of endothelial dysfunction).

Assessment will be conducted by UoD Immunoassay Biomarker Core Facility. Blood tests for cardiometabolic profiling may also be requested (via clinical laboratory, Clinical Research Centre/NHS Tayside) or collected from patient records with prior Caldicott Approval.

Samples will be stored in Division of Cardiovascular Research, School of Medicine, Ninewells low temperature freezers (-70oC).

Patient consent will be requested to store any surplus blood for future use which will require prior ethical approval.

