3.12 STUDY POPULATION

Our study populations are defined as follows

The study design is prospective study. All pregnant women will be included at the start except for exclusion criteria see (3.15). Outcome of pregnancy will be documented and participants will be placed into one of two groups retrospectively:

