6 STATISTICS AND DATA ANALYSIS

Descriptive statistics will be used in this study. To compare between groups, we will use a t-test and binary logistic regression, depending on the situation. Logistic regression analysis will be conducted to evaluate and account for any confounding factors. In order to validate the non-invasive techniques, a Bland-Altman analysis will be conducted to evaluate the comparability of the methods. Regression analysis to identify predictors of pregnancy outcomes. The Statistical analysis will be performed in SPSS (SPSS Statistics. 2022. Version 29.0.0.0. International Business Machines Corporation, New York, United States).

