6.2 PROPOSED ANALYSES

- **Study
- **Aim**: To investigate correlations between retinal imaging, ultrasound and blood sample biomarkers and future CVD risk factors in mid-late stages of gestation.
 - Hypothesis:

Cardiovascular Assessment:

Blood biomarker (sFlt-1, PIGF)) will correlate with retinal vascular changes and Dopple rultrasound indices, potentially predicting future CVD.

- **Methods**:
- Perform *correlational analysis* between retinal metrics and blood biomarkers to examine associations.
- Conduct *logistic regression analyses* to assess whether retinal imaging metrics in early pregnancy predict future CVD risk.
- *Multivariable regression modeling* to control for confounding factors such as maternal age, BMI, and pre-existing health conditions.

Data Protection Impact Assessment (DPIA)

- We aim to understand the link between retinal imaging biomarkers and cardiovascular function in gestational hypertension, predicting CVD risk factors and informing early interventions.

What will be the effect on data subjects?

-Positive Impact**: Early detection of risk factors for cardiovascular health, potentially improving maternal health management and long-term care.

What is the nature of the University's relationship with the data subjects?

- The University serves as the primary researcher and data controller, conducting the study with informed consent from participants. The relationship is one of informed, voluntary participation in medical research.

Are they expecting you to use their data in the way you've proposed?

- Yes, participants are fully informed through the consent process about the study's objectives, data collection, and how their data will be used for research on maternal and cardiovascular health.

Are there prior concerns with this proposed activity in the public domain that you are aware of?**

- Retinal imaging and biomarker studies in maternal health are generally well-accepted, though concerns about the use of sensitive medical data highlight the importance of rigorous data protection.

Is the University signed up to any codes of conduct in respect of the data processing?

- The University adheres to all GDPR guidelines and maintains compliance with institutional data protection policies, ensuring ethical handling and storage of sensitive health data.

Are there sufficient resources to meet the data security requirements for this type of processing?

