11.3 END OF STUDY

The end of study is defined as last patient visit and database lock. The Sponsor, CI and/or the SC have the right at any time to terminate the study for clinical or administrative reasons.

The end of the study will be reported to the Sponsor and REC within 90 days, or 15 days if the study is terminated prematurely. The CI will ensure that any appropriate follow up is arranged for all participants.

A summary report of the study will be provided to the Sponsor and REC within 1 year of the end of the study.

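### The future-CVD regression in section 6.2 has no outcome to model and, secondarily, nothing makes the database lock wait for delivery

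*Protocol*

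**What the plan says.** **Future CVD.** Section 6.2 commits to logistic regression "to assess whether retinal imaging metrics in early pregnancy predict future CVD risk". Its hypothesis adds that the blood biomarkers may predict later CVD. The synopsis lists "Long-term Cardiovascular Risk Indicators" among the secondary outcome measures, without definition or time point. In the same synopsis, the line "Follow up phase duration or specify none" is answered n/a and the clinical phase is during pregnancy. Under Blood Samples in section 3.5: "Once all the measurements have been taken, there will be no further requirements or assessments". Tables 1 and 2 in section 2 name only retinal imaging, endothelial biomarkers and Doppler, all measured in pregnancy.

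**Pregnancy outcome and study end.** Section 3.2 says pregnancy outcome will be tracked, and section 3.12 says "Outcome of pregnancy will be documented and participants will be placed into one of two groups retrospectively". Section 6 plans "Regression analysis to identify predictors of pregnancy outcomes". Visits are at weeks 10 and 20, each plus or minus 3 weeks, and one visit is enough (3.5). Section 9.1 defines GH as new onset after 20 weeks. Section 11.3 says "The end of study is defined as last patient visit and database lock". Section 6.3 keeps data checking open until missing values are corrected or clarified, and only then is the database locked.

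**The concern.** A logistic regression needs a binary dependent variable observed in the participants. For future CVD there is none, and the design has no point at which one could be observed. A later statistical analysis plan could define a model, but it could not supply data that were never collected. The risk is that in-pregnancy biomarkers are relabelled as CVD risk and the result is reported as prediction.

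The secondary point concerns the case/control label on which every group comparison rests. It becomes known only after the scheduled visits, yet the definition of the study's end does not mention delivery. If the lock came early, some women would have no known group, and cases are scarce: 11 are expected.

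**Working it through.** **1. Is there a CVD outcome?**

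- Synopsis: follow-up n/a, so no post-pregnancy time point.
- Section 3.5: no assessments after the measurements.
- Section 2, Tables 1 and 2: in-pregnancy measures only.
- Section 5.1: the data list covers history, medications, diagnosis, treatment and blood findings, with no post-pregnancy item.
- Synopsis, long-term CV indicators: undefined and absent from Tables 1 and 2.

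CVD events or post-pregnancy risk measures available: 0.

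**2. The plan's own recruitment figure.** Section 6.1 gives about 450 GH cases in 4500 births, and 450/4500 = 0.10. For 11 cases, 11/0.10 = 110 women. This reproduces. It counts women who *develop* GH, so it presumes ascertainment beyond the visits. Even with complete ascertainment, the binomial probability of at least 11 cases among 110 at 10% is 0.55.

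**3. Timing of the last visit against the outcome** (delivery at 40 weeks is an assumption).

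| Last visit (week) | Weeks until week 20 | Weeks to delivery | Weeks to 12 weeks postpartum |
|---|---|---|---|
| 7 | 13 | 33 | 45 |
| 13 | 7 | 27 | 39 |
| 17 | 3 | 23 | 35 |
| 20 | 0 | 20 | 32 |
| 23 | −3 (already past) | 17 | 29 |

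A woman seen only at the first visit is last seen 7–13 weeks before GH can be diagnosed under section 9.1.

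**4. Share undelivered at lock.** The entry for "Planned Trial/study Period" is 24 months, about 104 weeks. Accrual length and lock date are not stated. I assume uniform accrual over 18 to 23 months (78 to 100 weeks) and a last visit at week 20, so 20 weeks remain to delivery. With L weeks between the last scan and lock, the share is max(0, 20 − L) / accrual weeks.

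- Lock at month 24, 18-month accrual: L = 104 − 78 = 26, which exceeds 20, so 0%.
- Lock at month 24, 23-month accrual: L = 104 − 100 = 4, so (20 − 4)/100 = 16%. That is 0.16 × 110 = 17.6, about 18 women, and at 10% GH about 1.8 expected cases.
- Lock straight after the last scan (L = 0): 20/100 = 20% to 20/78 = 26%, or 22 to 28 women and 2.2 to 2.8 expected cases.

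**The case against.** **On CVD.** The aim in section 6.2 speaks of CVD risk factors in mid to late gestation. The study does collect possible in-pregnancy markers: carotid ultrasound and vessel elasticity (3.5), and perhaps cardiometabolic bloods. On that view the outcome is undefined rather than absent, and an unseen analysis plan could pick one. It stands that a named in-pregnancy marker could be kept as an outcome. It does not rescue the claim about future CVD, because association with a marker measured in the same pregnancy is not prediction of later disease.

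**On the study end.** Here the objection has more force.

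- Section 11.3 requires database lock as well as last visit, and section 6.3 holds the lock until missing data are corrected or clarified. If pregnancy outcome is a database field, a blank would be queried. A reader might infer that the study end cuts outcomes off; the documents do not say so. What is missing is an explicit requirement that lock wait for delivery.
- A reader might infer that women undelivered at lock become controls by default. No rule says that. Section 3.12 assigns groups once outcome is documented, and section 3.2 defines controls as women who do not get GH, which presupposes a known outcome.
- Sections 3.2, 3.14 and 6.1 allow recruitment of women already diagnosed, whose status is known at the visit. Sections 3.2 and 3.14 also mention late gestation, although the study matrix schedules no late visit. The exposure among cases is therefore lower than the 10% calculation suggests.
- The postpartum step in section 9.1 reclassifies women already diagnosed. It does not move normotensive women into the case group, so I have not used it to size the exposure.

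**Conclusion.** The future-CVD analysis is wrong as written. With no follow-up and no CVD or post-pregnancy risk measure, the study cannot support any conclusion about predicting future CVD. This needs no assumption beyond the protocol's own text.

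The study-end point is real but secondary: outcome tracking and a missing-data check are stated, but no section makes the lock wait for delivery. Its size rests on assumed accrual and lock dates. It is about 0–16% of women (0–18 of 110, fewer than 2 expected cases) if accrual runs 18 to 23 months and lock is at month 24. The 20–26% figure applies only if lock immediately follows the last scan, which nothing in the protocol requires. Both ranges are lower for cases recruited already diagnosed. They describe exposure, not a certain loss.

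**What to change.** **Future CVD.** Delete the future-CVD regression in section 6.2, the clause in its hypothesis about possibly predicting later CVD, and the long-term CV outcome in the synopsis. Make the dependent variable of the predictive model GH by delivery (yes/no), in line with the pregnancy-outcome regression already in section 6. Any in-pregnancy vascular marker kept as an outcome should be named as such and not described as predicting CVD. State whether women diagnosed before imaging enter the model, since for them it is not prediction.

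**Study end.** In section 11.3, define the end of study as the pregnancy outcome of the last participant ascertained from maternity records, followed by database lock. State that only women with a known outcome are classified as controls.

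**Cost.** Wording changes and record look-up, with no new visits. For the last woman enrolled, lock waits about 5 months from a 20-week scan to delivery, or up to about 8 months if 12-week postpartum status is also used. The Caldicott approval in section 3.2 is described for identifying participants, so its scope must be confirmed to cover outcome look-up. The study gives up a stated CVD aim, but one it could not have answered. With 11 expected cases the GH model must stay small: one retinal metric plus age, BMI and one term for pre-existing conditions gives 11/4 = 2.75 cases per term.

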6.3 MISSING DATA

Data entry and checking will be undertaken by a single entry with a second look. The data entry and checking process will be decided according to risk. Data that is recorded in the CRF that is not source document in itself will be consistent with the source documents or the discrepancies explained. Checks will be made on all missing values and values out with normal or expected ranges and that values entered are of the correct type: i.e. numerical instead of text. Logical checks will be performed to ensure consistent reporting between relevant fields and that there are no differences between fields. Data checking will continue until all missing data and/or inconsistent values have been corrected or clarified. When data checking is complete, with no outstanding data queries, the database will be locked, using the Protect Worksheet function of EXCEL, as FINAL RESULTS. The EXCEL spreadsheet will remain archived on the Dundee University secure server for 5 years for the retention of essential documents, thereafter it will be deleted.

6.4 TRANSFER OF DATA

Study data transcribed onto the paper CRFs will be transported from the site of the study visit, to the place of analysis and storage (University of Dundee), in a lockable case. Data transfer will follow the standard University of Dundee guidelines.

7 STUDY MANAGEMENT AND OVERSIGHT ARRANGEMENTS

7.1 STUDY MANAGEMENT GROUP

The study, no matter the number of participants or number of collaborating sites, should establish a study management group (T/SMG) to set and review the day to day management of the study. The T/SMG should include the CI, PIs and co-applicant.

A Delegation Log must be in place at each site.

The study will be co-ordinated by a Study Management Group (SMG), consisting of e.g. the grant holder Chief Investigator (CI), Principal Investigators (PI) ([name]).

7.2 STUDY STEERING COMMITTEE

No SC will be established, the remit will be carried out as part of the SMG.

7.3 DATA MONITORING COMMITTEE

No DMC will be established, the data monitoring for this study will be conducted as the remit as part of the SMG. Further data monitoring will be performed by University of Dundee Thesis monitoring committee and PhD exam for the principle investigator ([name])

7.4 INSPECTION OF RECORDS

The CI, PIs and all institutions involved in the study will permit study related monitoring, audits, and REC review. The CI agrees to allow the Sponsor or, representatives of the Sponsor, direct access to all study records and source documentation.

8 GOOD CLINICAL PRACTICE

8.1 ETHICAL CONDUCT OF THE STUDY

The study will be conducted in accordance with the principles of good clinical practice (GCP).

In addition to Sponsorship approval, a favourable ethical opinion will be obtained from the appropriate REC and appropriate NHS R&D approval(s) will be obtained prior to commencement of the study.

8.2 CONFIDENTIALITY AND DATA PROTECTION

The CI and trial staff will comply with all applicable medical confidentiality and data protection principles and laws with regard to the collection, storage, processing and disclosure of personal data.

The CI and trial staff will also adhere to the NHS Scotland Code of Practice on Protecting Participant Confidentiality or equivalent.

All trial records and personal data will be managed in a manner designed to maintain participant confidentiality. All records, electronic or paper, will be kept in a secure storage area with access limited to appropriate trial staff only. Computers used to collate personal data will have limited access measures via user names and passwords.

Personal data concerning health will not be released except as necessary for research purposes including monitoring and auditing by the Sponsor, its designee or regulatory authorities providing that suitable and specific measures to safeguard the rights and interests of participants are in place.

The CI and trial staff will not disclose or use for any purpose other than performance of the trial, any personal data, record, or other unpublished, confidential information disclosed by those individuals for the purpose of the trial. Prior written agreement from the Sponsor will be required for the disclosure of any said confidential information to other parties.

Access to collated personal data relating to participants will be restricted to the CI and appropriate delegated trial staff.

Where personal data requires to be transferred, an appropriate Data Transfer Agreement will be put in place.

Published results will not contain any personal data that could allow identification of individual participants.

The University of Dundee has a code of conduct and guidelines for data protection. The investigators all receive regular training in data protection measures. The University provides secure digital environment (Microsoft 365). There are data protection officers in TASC, University of Dundee who the research team can consult. The responsibility lies with all of the research team.

Studying Pregnancy's VAscular and Retinal Changes (SPARC), Non CTIMP Protocol (SPARC) During Preg <v1.0 13/3/2025>; IRAS: 347685

There are procedures in place if there is a data breach and these will be followed.

